## 6) Framework

The superiority hypothesis testing framework will be used, testing whether exposure to the intervention results in better outcomes than exposure to the control arm. Comparisons will be presented as differences between arms in changes in outcomes from baseline to endline.

## 7) Statistical interim analyses and stopping guidance

- a. Information in interim analyses specifying what interim analyses will be carried out and listing time points
  - i. None planned
- b. Any planned adjustment of the significance level due to interim analysis
  - i. No
- c. Details of guidelines for stopping the trial early

- i. None

## 8) Timing of final analyses

Analysis is planned to begin in March 2025 upon completion of all field data collection in February 2025, when the 6-month follow-up of all participants is done. Analysis to evaluate the durability of the intervention will commence after the end of 12-months of follow-up of the intervention arm (July 2025).

## 7) Timing of outcome assessments

Research staff will administer surveys, dietary recall, anthropometric evaluations, and blood draw at baseline and at 6 months in both study groups. Additional evaluations will be done only in the intervention arm at 12 months. Data will be collected within a window period around each data collection time point of up to 2 months.

# Section 4: Statistical Principles

## 1) Confidence intervals and P Values

- a. **Level of statistical significance.** No significance testing will be conducted unless required by a journal. We will report 95% confidence intervals and exact p-values (or  $p<0.001$ ).
- b. **Description and rationale for any adjustment for multiplicity and, if so, detailing how the type I error is to be controlled.** The primary outcomes were established in the protocol, and thus no adjustments will be made for multiplicity.
- c. **Confidence intervals to be reported.** 95% confidence intervals will be reported alongside exact p-values.

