## 2) Objectives

**Aim 1:** To determine the impact of CHEFS-DM on glycemic control and other cardiometabolic outcomes. The hypothesis is that CHEFS-DM will improve hemoglobin A1c (primary outcome), dyslipidemia, and health-related quality of life (HRQoL); blood pressure (BP) and acute care utilization; and improve diabetes medication adherence (secondary outcomes). Participants will be randomized to intervention versus control.. Data collection will include surveys, anthropometry, 24-hour dietary recalls, BP measures, medical record review, and blood draws. Characteristics of those most likely to benefit from CHEFS-DM will be described (e.g., poor T2DM control, gender).

**Aim 2:** To determine the impact of CHEFS-DM on intermediate outcomes that may mediate any impact of CHEFS-DM on T2DM health. Using our novel conceptual model, the hypothesis is that that CHEFS-DM will improve food insecurity (proximal intermediate outcome) which in turn will lead to improvements in nutritional (e.g., improved diet, body mass index), mental health (e.g., less diabetes distress, depression), and behavioral (e.g. improved medication adherence, diabetes self-management, and clinic attendance) paths (distal intermediate outcomes). Together these will improve T2DM control, cardiometabolic health, and HRQoL. Identifying the predominant causal paths will enable to further tailor the program to enhance impact during future implementation.

**Aim 3.** To determine the cost-effectiveness and sustainability of CHEFS-DM and obtain information to inform scale-up. a) The cost per quality-adjusted life year gained will be calculated; b) Whether any improvements in the intervention arm were sustained over 12 months of follow-up will be assessed; and c) A process evaluation will be performed, collecting qualitative and quantitative data with study participants and staff to determine what worked and did not work to guide future intervention scale-up efforts. The hypothesis is that the intervention may be cost-effective and possibly cost saving, and that health benefits will be sustained at 12 months.

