## 5) Sample size

The sample size was determined based on power calculations on our primary outcome (HbA1c) and estimated attrition based on our previous studies in this population. Power calculations were based on standard deviations (SD) for changes in baseline to follow-up from our prior pilot study and assumed 80% power for a one-sided test at alpha of 0.05 corresponding to our hypothesis that the intervention would improve glycemic control and other outcomes. With the outcome of change in percent HbA1c from baseline to follow-up, using a SD of the change of 1.3937 for a minimum important difference of 0.5 in the change, the sample size needed is n=196 (n=98 in each of the two study arms). This sample size also provides 80% power for differences between arms in change in diabetes distress of 0.256 points, change in food insecurity of 1.3 points, and proportion at follow-up of 0.16 (e.g., 0.36 vs. 0.20) or greater for any binary outcome such hospitalization or emergency department visit. Anticipating attrition of 20%, the total sample size needed at recruitment would be at least 245. To be conservative, we enrolled 281 participants to account for the possibility of higher attrition than anticipated.

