## Section 6: Analysis

### 1) **Outcome definitions**

Primary Outcome Measures:

1. Hemoglobin A1c. At baseline and six months, all participants will undergo the blood draw; at twelve months, the blood draw will be implemented in the intervention arm only. The change on HbA1c from baseline to six months by study arm will be reported.
2. Food security. Food insecurity will be measured with the adult version of the USDA Household Food Security Survey Module (HFSSM), validated in many populations. The score ranges from 0 to 10 . Higher scores indicates higher severity of food insecurity. The change in the food insecurity scores from baseline to six months by study arms will be reported.

Secondary Outcome Measures:

1. Glucose control. The change in the proportion of participants with glucose control, defined as HbA1c <9%, from baseline to six months by study arms will be reported.
2. Low food security. Food security as a binary response will be assessed, identifying a participant having low or very low food security or food security (food security or marginal food secure) by study arm.

3. Systolic and diastolic blood pressure. Changes in the average of three repeated measurements of systolic and diastolic blood pressure (mmHg) from baseline to six months by study arm will be reported.
4. Medication adherence. A Single-Item Rating Visual Analogue Scale (range 0-100) for medication adherence will estimate the percentage of medications taken in the past month and is reliable and valid, including in low-literacy populations. The change in medication adherence (percentage points) from baseline to six months between intervention and control arms will be reported.
5. Acute care utilization. Information on acute care utilization (emergency department and urgent care) by self-report and/or medical record review will be collected. The proportion of participants that used acute health care from baseline to six months by study arm will be reported.
6. Hospitalization. Information on hospital admissions will be collected by self-report and/or medical record review. The proportion of participants with at least one event of hospitalization will be reported by study arm.
7. Missed outpatient visits. Information on missed outpatient visits will be collected by self-report and/or medical record review. The proportion of participants that missed at least one outpatient visits from baseline to six months will be reported.

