**b. Analyses for Aim 2 (intermediate outcomes and mediation):**

The hypothesis is that the intervention will improve food insecurity (proximal intermediate outcome) and in turn nutrition (e.g., improved diet quality, BMI), mental health (e.g., less diabetes distress, depression) and health behaviors (e.g., medication adherence, diabetes self-management, clinic attendance) (distal intermediate outcomes) as suggested by our conceptual framework.

As described in Aim 1, analyses will be done for the intermediate outcomes using an analysis of covariance with linear or logistic models as appropriate. Statistical mediation from the intervention to the primary and secondary outcomes by the intermediate outcomes will be assessed first with the Stata sem procedure using traditional path analytic methods, testing for possible interactions between exposure (i.e., arm) and mediators, and then with Mplus using the causal inference method of Valeri and Vanderweele, which yields optimal estimates of indirect effects in the presence of non-continuous outcomes, interactions, and clustered data.

c. **Analyses for Aim 3 (cost-effectiveness analysis and process evaluation).**

To understand the relative value of CHEFS-DM in comparison to other health interventions, the incremental CE ratio (ICER) will be computed, defined by the difference in the per-capita intervention cost divided by the difference in the average intervention effectiveness.

The cost-effectiveness ratio is given by  $ICER = (\mu T - \mu C) / (\delta T - \delta C)$ , where  $\mu T$  is the per-capita cost of the treatment,  $\mu C$  is the per- capita cost of the control,  $\delta T$  is the health status of the treatment, and  $\delta C$  is the same measure for participants in the control group. To account for uncertainties in costs or effectiveness, estimates across a range of assumptions regarding future costs and health effects will be computed.

Confidence intervals for the ICER measures will be calculated using bootstrap methods. In terms of timeframe, the cost savings and health improvements at 6 and 12 months through direct measurement will be estimated. Additional analyses will be considered extrapolating cost savings to future periods under different assumptions of how long those changes last and impacts informed by the literature (e.g. the reduction in DM complications attributable to improved glycemic control).

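### HbA1c and food security are both listed as primary, other sections name HbA1c alone, no success rule is given, and multiplicity is waived for a reason that does not control error

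*Combined protocol and SAP*

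**What the plan says.** **Two primaries.** Section 6, 1) Outcome definitions, numbers two items under its primary heading. The first is HbA1c. Under the second, "Food insecurity will be measured with the adult version of the USDA Household Food Security Survey Module", with the six-month change in score compared by arm.

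**One primary.** Section 2, 2) Objectives, Aim 1, says "The hypothesis is that CHEFS-DM will improve hemoglobin A1c (primary outcome), dyslipidemia" and continues with further outcomes. Section 3, 5) Sample size, rests on "power calculations on our primary outcome (HbA1c", in the singular. The Aim 1 text in Section 6, 2) Analysis methods, also attaches the primary label to HbA1c only.

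**Food insecurity as intermediate.** Aim 2 of the Objectives says the programme "will improve food insecurity (proximal intermediate outcome"), and the Aim 2 analysis text repeats that label.

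**Signs the other way.** The Sample size section also gives power for a "change in food insecurity of 1.3 points". Section 6, 6) Additional analyses, picks out HbA1c and food security together for the durability analysis.

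**Testing and multiplicity.** Section 4, 1) Confidence intervals and P Values, item a, says "No significance testing will be conducted unless required by a journal", while promising 95% intervals and exact p-values. Item b says "The primary outcomes were established in the protocol, and thus no adjustments will be made for multiplicity". Section 3, 6) Framework, sets a superiority hypothesis-testing framework, and the Sample size section assumes a one-sided test at 0.05.

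**The concern.** There are two linked problems.

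First, success is undefined. The intervention supplies food, so better food security with no HbA1c effect is a plausible result. The plan does not say whether that would be a positive trial. This is not a false-positive problem, because a real gain in food security would be a true finding. The risk is that the rule gets chosen once the results are known.

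Second, the reason given for making no adjustment does not support it. Pre-specification fixes which outcomes are examined. It does not fix the chance that at least one of two primaries looks positive when neither has changed. Some rules need no adjustment, such as requiring both outcomes or testing in a fixed order, but the plan adopts none of them.

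**Working it through.** **Inputs.** From Section 3, 5) Sample size: difference 0.5, SD of change 1.3937, one-sided alpha 0.05, power 80%, 98 per arm (196), 20% attrition, 245 to recruit. From Section 7: 156 intervention and 125 control participants enrolled. The documents give no correlation between the two outcomes, so every correlation below is an assumption.

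**The plan's own figure.** n per arm = 2 × [(1.645 + 0.842) × 1.3937 / 0.5]² = 96.1, so 97 per arm and 194 in total, against 196 stated. Then 196 / 0.80 = 245, as stated. At 98 per arm a one-sided t test has 80.4% power. The stated size is therefore reproduced within rounding, and it gives HbA1c the full one-sided 0.05.

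**Chance of a false claim, by rule.** Neither outcome truly changes unless noted. Test statistics are taken as bivariate normal.

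| Rule | Independent | Correlation 0.5 | Correlation 0.7 |
|---|---|---|---|
| Either outcome, one-sided 0.05 | 1 − 0.95² = 9.75% | 8.8% | 8.0% |
| Either outcome, two-sided 0.05 | 9.75% | 9.1% | 8.4% |
| Either outcome, benefit claims from 95% intervals only (one-sided 0.025 each) | 1 − 0.975² = 4.9% | 4.5% | 4.2% |
| Both must succeed, one-sided 0.05 | 0.05² = 0.25% | 1.2% | 2.0% |

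If both must succeed and one outcome truly changes, the false-claim rate can rise to 5% but no further.

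**Power for HbA1c.** t test with SD 1.3937 and difference 0.5. Enrolled arms after 20% attrition: 156 × 0.8 ≈ 125 and 125 × 0.8 = 100.

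| Evaluable per arm | One-sided 0.05 | One-sided 0.025 |
|---|---|---|
| 98 / 98 | 80.4% | 70.5% |
| 125 / 100 | 84.6% | 75.9% |

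The right-hand column is the worst case for HbA1c under an equal alpha split or Holm within a one-sided 0.05 family. It is also HbA1c's power if the 95% interval, rather than the one-sided 0.05 test, is the claim standard. In a fixed sequence with HbA1c first, the left-hand column applies unchanged.

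**Joint power if both must succeed.** With the 80% stated for each outcome at 98 per arm: 0.80² = 64% if independent, and 69% at correlation 0.5.

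**The case against.** The strongest reply is that the plan mostly disclaims testing. It reports estimates with 95% intervals, and if benefit is claimed only from those intervals, two unadjusted primaries give 4.9% or less, which is within the design's one-sided 5%. On that reading no adjustment is needed. This stands as arithmetic, and it is why 9.75% is a conditional figure. It does not rescue the plan. The disclaimer lapses if a journal asks for tests, p-values will be reported anyway, the Framework and Sample size sections assume a one-sided 0.05 test, and the stated reason for the waiver is pre-specification rather than the interval argument. A report based only on estimates would still need to say which outcome is primary.

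A second reply is that an intermediate outcome is a place in the causal path, not a rank, and that the primary labels under Aim 1 may mean primary for that aim. This has some force: an outcome can be both a primary and a mediator. It does not explain the singular wording in the Sample size section, and it supplies no success rule.

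A third reply is that both outcomes will be reported whatever happens. That limits selective reporting but not selective emphasis.

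A fourth is that the power costs are conservative, and this is correct. The planned ANCOVA on baseline would do better than a t test on change. If baseline and change correlate at 0.3 to 0.5 (assumed), HbA1c power at one-sided 0.025 is 75–82% at 98 per arm and 80–87% at 125/100. Joint power at 125/100 is about 71% if independent and 75% at correlation 0.5, using the food-insecurity SD of about 3.66 implied by the 1.3-point figure. The costs quoted for the fix are therefore upper bounds in these respects.

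**Conclusion.** The concern holds and should be fixed. The current text conflicts on whether food security is primary, and the multiplicity waiver rests on a reason that does not control error. The trial's false-claim rate cannot be stated: it lies anywhere from at most 5% to 9.75%, depending on a rule the plan does not give. Inflation above 5% arises only if either outcome suffices at 0.05. The values between those limits rest on assumed correlations. The planned estimates and intervals remain valid; what is undefined is which result would support a confirmatory claim.

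**What to change.** Before outcomes are analysed by arm:

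1. Make the Objectives, Sample size, Outcome definitions and Analysis methods (Aims 1 and 2) agree on whether food security is primary.
2. Replace the rationale in Section 4, 1) b with one stated rule:
   - **HbA1c is the sole primary**, as three sections already say. If a confirmatory claim on food security is wanted, test it after HbA1c, in fixed sequence at full alpha. HbA1c loses no power, but food security cannot be claimed as confirmatory if HbA1c is null.
   - **Both are primary and either suffices.** Use Holm or Hochberg. Within a one-sided 0.05 family, worst-case HbA1c power is about 71% at 98 per arm, or 76% for the enrolled arms after 20% attrition.
   - **Both are primary and both must succeed.** No adjustment is needed. State the joint power, about 64–69% at 98 per arm.
3. Say whether the one-sided 0.05 test or the 95% interval supports a claim.
4. Record any change of designation as a dated amendment with its reason, since enrolment has closed.

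This needs no new data and leaves the planned estimates and intervals as they are. Version 2 is dated 02/05/2025 and analysis was planned from March 2025, so the amendment should state whether any outcome data by arm had been seen when the rule was set.

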## 2) Adherence and protocol deviations

- a. **Definition of exposure to the intervention and how this is assessed including extent of exposure:**

Adherence to the intervention will be assessed through the following mechanisms:

- i. Counseling: Attends at least the first individual counseling session (out of 2)
- ii. Group education: Attends at least 50% of group education sessions (2 out of 4).
- iii. Food: Receive at least 60% of weekly food allotment.

- b. **Description of how adherence to the intervention will be presented – We**  
will Adherence to the intervention will be presented through a brief description in

the narrative summarizing the percent of weekly engagement with food deliveries/pickups,  
% of food allotments received, and % of food reported eaten, as well as % of counseling sessions and education sessions attended.

c. **Protocol deviation.** The following are pre-defined minor protocol violations:

- i. Participants that for any reason are not seen within the visit window (up to two months later).
- ii. Investigators miss giving a questionnaire or a section of the questionnaire to the participant, including the dietary recall questionnaire.
- iii. Investigators miss recording or performing any anthropometric / blood pressure evaluations or blood draw or done outside of visit window.

The following are pre-defined major protocol violations:

- i. Participants that are mistakenly enrolled in the study without meeting the inclusion criteria.
- ii. Participants in the control arm receiving meals or groceries from Project Open Hand during the active intervention period (baseline to 6 months).
- iii. Participants for whom informed consent was not obtained prior to any study- specific tests/procedures.
- iv. Lapse in study approval

The number (and percentage) of participants with major and minor protocol deviations will be summarized by arm with details of type of deviation provided. The participants that are included in the ITT analysis data set will be used as the denominator to calculate the percentages. No formal statistical testing will be undertaken.

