Control condition. Control participants will receive the standard of care as offered by clinical partners to all T2DM participants, including referral to nutritional counseling, T2DM support groups, and participation to local diabetes self-management programs. Control participants are also often provided referral information for locally available food support services in the region that provide diabetes-appropriate foods. After 6-months, the control arm will have the opportunity to receive diabetes-tailored food support from POH along with nutritional counseling, regardless of whether they meet regular POH eligibility criteria. The services that the control group will receive after the six-month period will be similar to what the intervention group receives during the intensive CHEFS-DM intervention - 6-months of food sufficient to meet 67% of their daily requirements, video recordings of the 4 CHEFS- DM intervention nutrition education classes and access to a POH RD at their request.

Given that POH could not easily absorb a large number of additional new clients in a relatively short time frame, the wait time is also in line with programmatic considerations.

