## 5) Data collection

Follow-up will be broken up into two phases. From baseline to six months, the CHEFS-DM intervention will be implemented, and researchers will follow both intervention and control arm participants (n=281 (actual)). After the end of the six-month follow-up, the intervention arm will transition to receiving standard POH services (comprising 33% to 67% of daily energy requirements depending on health status), and will be followed for an additional six months, to assess the extent to which any health benefits are sustained at 12 months (n=156). Hence, control arm will be followed for 6 months and participate in two assessments, and the intervention arm will be followed for 12 months and participate in three assessments.

At baseline and 6 months for all participants and at 12 months for intervention arm, the following data will be collected:

a) Structured interviews (baseline, 6 and 12 months). Trained UCSF research assistants (RAs), including Spanish/English bilingual RAs, will administer the structured interview either in person or over the phone and/or zoom, depending on public health protocols and acceptability of in-person visits to participants due to COVID-19. When visits are conducted in-person, interviews will take place in private offices at POH, in a private room at a partner clinic (if available), in a private location at a community space (e.g. library, community center), or at a private location of the participants choosing (e. g. home visit).

The content of the interviews will cover:

- Socio-demographic information.
- Food insecurity and diet quality
- Physical activity
- Mental health (e.g., depressive symptoms, diabetes distress and social support, self- efficacy for following T2DM recommendations).
- Adherence to T2DM medications.
- Health care utilization (e.g., missed clinic visits, acute care use (hospitalizations and emergency department visits)).
- Health-related quality of life.
- Medication inventory (for cardiometabolic conditions only).
- Diabetes co-morbidities (e.g. nephropathy, retinopathy).
- Economic information (e.g. economic impacts of COVID-19, household expenditures on food).

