- d) Blood draws (baseline, 6, and 12 months): Participants will undergo a blood draw (testing a lipid panel, and HemoglobinA1c) at one of 28 Quest Diagnostics labs in San Francisco or Alameda counties Phlebotomy will be performed using universal precautions. Date and time of phlebotomy, and specimen number will be recorded in a participant log. Specimens will be aliquoted and stored at -70°C using standard universal precautions. Data will be received from Quest Diagnostics in the form of a spreadsheet which can be easily merged with other study data by participant ID or will be accessed by UCSF staff using the secure Quest Diagnostics HIPPA-compliant online portal. At baseline and six months, all participants will undergo the blood draw; at twelve months, the blood draw will be implemented in the intervention arm only.
- e) 24-hour Dietary Recall (baseline and 6 months). Dietary intake will be assessed via 24-hour dietary recalls by UCSF RA trained by registered dietitians using the National Cancer Institute's Automated Self- Administered 24-hour Dietary Recall (ASA24). Participants will complete two unannounced recalls (one weekday and one weekend day) during a one-week period. In total, participants will complete four recalls: 2 at baseline and 2 at 6-month follow- up. RA's will inform the participant of which week the calls will be attempted. Previous work has indicated that lower income or older adults may need additional assistance with completing the ASA24, therefore the questions will be administered over the phone or in person (if COVID permits), using strategies to ensure the collection of dietary data is accurate and does not burden the participant. The 24-hour dietary recall will be conducted at baseline and six-month follow up.
- f) Medical record review (baseline, 6, and 12 months). Medical records will be used

during recruitment to confirm T2DM diagnosis, to confirm participant HbA1c, preferentially greater than or equal to 6.5%, and to determine whether a patient has controlled or uncontrolled T2DM using latest HbA1C test result. Medical record review is also being used to collect follow-up HbA1c data if completing a blood draw is not possible during follow-up, if medical record A1c is available within the assessment time frame, and with the consent of the participant.

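### The control-arm contamination rule stops at month 6, although an in-window 6-month assessment may come up to two months later, when controls may already be receiving Project Open Hand (POH) food

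*Combined protocol and SAP*

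**What the plan says.** Five provisions of the combined protocol and SAP bear on this point.

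- **Start of control food** (Section 3, Intervention description, control condition): "After 6-months, the control arm will have the opportunity to receive diabetes-tailored food support from POH along with nutritional counseling". The amount is given as "6-months of food sufficient to meet 67% of their daily requirements", and the services are described as similar to those of the intervention arm.
- **Assessment window** (Section 3, Timing of outcome assessments): "Data will be collected within a window period around each data collection time point of up to 2 months". The list of minor violations in Section 4 gives the direction: "Participants that for any reason are not seen within the visit window (up to two months later".
- **Substitute HbA1c** (Section 3, Data collection, item f): if a follow-up blood draw is not possible, a medical-record value may be used, with the participant's consent, "if medical record A1c is available within the assessment time frame".
- **Contamination** (Section 4, Adherence and protocol deviations): major violation (ii) is "Participants in the control arm receiving meals or groceries from Project Open Hand during the active intervention period (baseline to 6 months".
- **Per-protocol set** (Section 4, Analysis populations): controls with both evaluations are kept unless they have a major violation.

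The primary analysis is by intention to treat. Both primary outcomes, HbA1c and the food security score, are changes from baseline to six months.

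**The concern.** The contamination period ends on a fixed calendar point. The outcome is measured on a date that differs between participants and may be later. Between the two lies a gap of up to about two months in which a control may receive POH food and still be measured in window.

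The per-protocol analysis is where a reader will look for a comparison free of control exposure. As written, it need not be one, and the deviation table would not reveal this. Any such exposure would also be present in the intention-to-treat contrast for HbA1c and food security. If the intervention works, it would tend to make the arms look more alike.

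The substituted HbA1c adds to the difficulty. Its date is set by routine care, so a practice of scheduling the study visit before food release would not by itself ensure that the value predates food.

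**Working it through.** **Following the rules literally.** Take a control who starts POH food at month 6 and has blood drawn at month 7.5.

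1. Is the visit in window? Yes: it is 1.5 months late, and up to two months is allowed. There is no minor violation.
2. Is the food a major violation? No: it came after month 6, and violation (ii) covers baseline to 6 months.
3. Is the participant dropped from the per-protocol set? No: there is no major violation.
4. Does another rule put assessment before food? None was found in the control-condition, data-collection, timing or deviation text.
5. Does another planned analysis pick it up? None is defined by visit timing or control exposure, and Section 6, Sensitivity analysis, rules out any beyond those described. The 6-month interview item on free food excludes POH.

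**The plan's own sample size.** Inputs from Section 3, Sample size: SD of change 1.3937, difference 0.5, one-sided alpha 0.05, power 80%.

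- n per arm = 2 × (1.645 + 0.842)² × 1.3937² / 0.5² = 96.1, so 97. The plan states 98, which is within rounding.
- Recruitment at 20% attrition: 196 / 0.80 = 245, as stated.

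**Illustration of dilution.** Let f be the share of controls exposed before assessment and g the share of the full effect that they had gained by then. Then:

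diluted difference = 0.5 × (1 − f × g)

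Neither f nor g is in the documents. I assume g = 1/3, and f = 0, 10% or 30%. Power is for a one-sided two-sample t-test at 0.05. The second set of sizes applies the planned 20% attrition to the actual arms (Section 7): 156 × 0.8 ≈ 125 intervention and 125 × 0.8 = 100 control.

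- Standard error at 98 per arm: 1.3937 × √(2/98) = 0.199
- Standard error at 125 and 100: 1.3937 × √(1/125 + 1/100) = 0.187

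| f | Diluted difference | Power, 98 per arm | Power, 125 and 100 |
|---|---|---|---|
| 0 | 0.500 | 80.4% | 84.6% |
| 10% | 0.483 | 78.1% | 82.4% |
| 30% | 0.450 | 72.8% | 77.5% |

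These are unadjusted comparisons, as in the plan's own calculation. The primary model also adjusts for baseline, so the table shows scale and is not a forecast.

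No such illustration is given for food security. The recall period of the outcome scale is not stated, so there is no basis for assuming how quickly the score would respond.

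**The case against.** **This is silence, not contradiction.** All the rules can hold together if food was released only after the 6-month visit. Section 3 describes control food as an opportunity that follows a waiting period tied to POH's capacity, not as an automatic start at month 6. This stands in part. A reader might infer that controls were in fact contaminated, and nothing in the documents shows that. The cut-off nonetheless misclassifies any control who was fed before an in-window assessment, and a visit-first practice would not cover a medical-record HbA1c.

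**The reach is limited.** Redefining violation (ii) changes the deviation table and the secondary per-protocol set, not the intention-to-treat result. Bias in that result would most likely be towards no difference, so the gap gives no reason to suspect a falsely favourable finding. This stands.

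**The exposure can be found.** Weekly POH records of food collected or delivered are planned for each participant (Section 3, Data collection, item h). It would be too strong to say that the trial cannot detect the problem; it is the violation label that misses it. Whether the records cover controls after month 6 is not stated.

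**The intervention arm.** A reader might infer that late visits also weaken the intervention arm, because "the intervention arm will transition to receiving standard POH services". That sentence begins by placing the transition after the end of the six-month follow-up, which may mean the completed visit rather than the calendar date. The documents do not settle this, so no second source of dilution is claimed.

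**Larger losses of power.** If every control were exposed and g were 1/3, power at 98 per arm would be about 51%. That needs every control to be assessed late, to accept optional food and to have received it first. Nothing in the documents supports such a case.

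**Conclusion.** The gap in the rules is real and rests on the text alone. A control who receives POH food between month 6 and an in-window assessment is neither recorded as a violation nor removed from the per-protocol set, and no provision states that assessment comes first.

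Whether this occurred, and in how many controls, is unknown, so the size of any dilution cannot be computed from the documents. Under the assumed 10% to 30% exposed with one third of the effect gained, the loss is about 2 to 8 percentage points of power at 98 per arm (80.4% to 78.1% or 72.8%), and about 2 to 7 points at 125 and 100 (84.6% to 82.4% or 77.5%). If food was always released after each control's outcome measurements, including any substituted HbA1c, the effect is nil and only the wording needs repair.

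The correction should be made before analysis because it is specific and inexpensive.

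**What to change.** 1. Reconcile the control-condition, medical-record, timing and deviation text by stating the order of the 6-month assessment and control food, including for a substituted HbA1c.
2. Define violation (ii), and the matching per-protocol exclusion, as any POH food received before that participant's own 6-month HbA1c measurement (for food security, before the interview). Date the food from the weekly POH records where these cover controls, and say what is done where they do not.
3. Report the number of controls exposed before assessment, separately for HbA1c and food security.
4. Add one supportive sensitivity analysis of both primary outcomes that sets those measurements aside. Intention-to-treat stays primary.
5. Clarify whether the intervention arm's transition is tied to the six-month date or to the completed visit.

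**Cost.** SAP wording and a merge of dates, with no new data collection if the POH records include controls. The sensitivity analysis loses some participants and may introduce selection, because late attendance and uptake of food both arise after randomisation. It should therefore be labelled supportive and read alongside the primary result.
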